7.1.2.1 Eligibility screening

Dosing with chemotherapy may begin while FLT3 mutation results are pending. FLT3 mutation results from the central laboratory must be received by Day 8 and will be used to determine if the subject is eligible for randomization and to receive midostaurin/placebo.

Following registering in the IRT for screening, patient eligibility will be checked once all screening procedures are completed (except FLT3 status). The eligibility check will be embedded in the IRT system.

Please refer and comply with detailed guidelines in the IRT manual.

7.1.2.2 Information to be collected on screening failures

A patient who signs an informed consent but fails to begin chemotherapy for any reason will be considered as a screen failure. The reason for not being started on chemotherapy will be entered on the Disposition CRF. The demographic information, informed consent, and Inclusion/Exclusion CRF must also be completed for Screen Failure patients. FLT3 data will be collected for all patients including screen failures. No other data will be entered into the clinical database for patients who are screen failures, unless the patient experienced a Serious Adverse Event during the Screening Phase (see [Section 8](#) for SAE reporting details). If the patient fails to be randomized, the IRT must be notified within 2 days of the screen fail that the patient was not randomized.

Information to be collected on patients who failed to be randomized

Patients who are determined to have a positive or unknown FLT3 mutation status at Day 8 of the 1st cycle of induction will not be randomized and will then be discontinued from the study.

In addition to data collected at screening, the reason for not being randomized will be entered on the disposition CRF, and AEs/SAEs will also be collected, if applicable.

No other data will be collected for those patients.

7.1.2.3 Patient demographics and other baseline characteristics

The data to be collected on subject characteristics at screening includes:

- Diagnosis and extent of cancer (WHO and French American British (FAB) classification)
- Demography (Age, gender, race and ethnicity, or as allowed by local regulations)
- Cytogenetics
- Medical history
- Prior antineoplastic medications
- Prior and concomitant medications

Assessments to be performed at screening/baseline include:

- Physical examination (i.e., performance status Eastern Cooperative Oncology Group (ECOG), height, weight, vital signs)
- Extramedullary involvement

- Laboratory assessments (i.e., hematology, chemistry, coagulation, urinalysis, serum pregnancy test)
- Cardiovascular assessments (i.e., ECG; ECHO or MUGA)
- Chest x-ray
- Assessment of disease (in blood and bone marrow)
- Biomarker assessments in blood and bone marrow (for FLT3 mutation status [REDACTED])

7.1.3 Treatment period

Patients will be assigned on Cycle 1 Day 8 of induction therapy to midostaurin or placebo using a stratified randomization according to age.

- Study treatment will begin on Day 1 of Cycle 1 with chemotherapy: daunorubicin from Day 1 to Day 3 and cytarabine from Day 1 to Day 7. Study treatment will continue on Day 8 with midostaurin/placebo until 48 hours prior to start of next cycle.
- Chemotherapy and midostaurin/placebo will be administered as indicated in [Table 7-1](#) and until the subject experiences any of the following: persistent disease, relapse as determined by investigator, unacceptable toxicity that precludes further treatment, pregnancy, start of non-protocol anti-cancer therapy, discontinuation at the discretion of the Investigator or patient, loss to follow-up, death, or study termination by the Sponsor.

Visit frequency

- Induction phase cycle 1: most assessments will be scheduled once or twice per week until hematology recovery. This cycle may be longer than 28 days (until hematology recovery occurs), and the assessments will be performed accordingly but cannot be longer than 43 days (28 days plus up to 14 additional days for blood count recovery) in total. If the patient has evidence of persistent leukemia on a bone marrow evaluation at the end of the first induction cycle, then a second cycle of induction therapy will be administered.
- Induction phase cycle 2: assessments will be the same as for Cycle 1, except for the PK [REDACTED] and study drug dispensation. The maximum length of induction cycle 2 is 50 days (28 days plus up to 21 additional days for blood count recovery). For details of assessments in induction Cycles 1 and 2, refer to [Table 7-1](#).
- Patients who achieve a CR or CRi with adequate blood count recovery will continue with consolidation therapy for 3 to 4 cycles with a maximum length of 50 days (28 days plus up to 21 additional days for blood count recovery) each. Patients achieving CR/CRi with adequate blood count recovery after induction cycle 1 will have 4 cycles of consolidation therapy and patients achieving CR or CRi with adequate blood count recovery after the second cycle of Induction will have 3 cycles of consolidation therapy.
- Patients who remain in CR or CRi with adequate blood count recovery after consolidation therapy will begin post-consolidation therapy for up to 12 cycles of 28 days each. Post-consolidation therapy will begin immediately (i.e. up to 48 hours) after the last dose of midostaurin/placebo during the last cycle of consolidation therapy and no later than 50 days after the start of the last consolidation cycle. Patients who remain in remission after 12 cycles of post-consolidation therapy will continue in post-treatment follow-up.

- Patients in CR or CRi with adequate blood count recovery may proceed to HSCT and will enter the post-consolidation phase within 48 hours after the end of the consolidation phase.

Time windows for scheduling assessments

- Every effort should be made to follow the schedule of assessments as described in the protocol and especially during the induction and consolidation cycles for PK and ECG assessments.
- All other assessments have a ± 5 days window, unless otherwise indicated.
- Patients who discontinue study treatment must have an End of Treatment (EOT) visit performed ≤ 7 days after stopping study treatment.

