Study design	
This is a multi-center, multinational, randomized, double-blind Phase III study using a group sequential design with two interim analyses. The primary endpoint is EFS as per investigator assessment and is defined as the time from randomization to failure to achieve CR or CRi with adequate blood count recovery (i.e., neutrophils $\geq 1.0 \times 10^9/L$ and platelets $\geq 50 \times 10^9/L$) in induction phase, relapse from CR or CRi with adequate blood count recovery or death due to any cause whichever occurs first.
 
Overall survival (OS) is the key secondary endpoint and is defined as the time from randomization to death due to any cause. OS will be hierarchically tested if the EFS shows significant improvement in the second interim analysis or in the final analysis.
 
Patients will be stratified according to Age (<60 vs. ≥ 60 years)
 
Patients within each stratum will be randomized in a 1:1 ratio into one of two treatment arms: Midostaurin + chemotherapy or Placebo + chemotherapy
 
The study will consist of the following phases: Screening/randomization phase: Patients having signed informed consent will be screened for eligibility criteria. Patients will start treatment with chemotherapy at day 1 and will be randomized at day 8.
 
Induction phase: All patients will receive at least one cycle of induction therapy with continuous infusion cytarabine and daunorubicin or idarubicin (induction 1). Patients not achieving CR or CRi with adequate blood count recovery after Induction 1 will receive a second cycle with intermediate-dose cytarabine and daunorubicin or idarubicin (induction 2). Patients not achieving CR or CRi with adequate blood recovery after induction 2 will discontinue study treatment and will be followed for survival. Patients achieving CR or CRi with adequate blood count recovery after induction 2 will enter the consolidation phase.
 
Consolidation phase : Patients achieving CR or CRi with adequate blood count recovery after induction with one or two cycles will proceed to consolidation therapy with either 3 or 4 cycles of intermediate-dose cytarabine, or to Hematopoietic Stem Cells Transplantation (HSCT) with or without preceding consolidation cycles.
 
Post-consolidation phase: Patients achieving CR or CRi with adequate blood count recovery at the end of the consolidation phase will receive 12 cycles (28 days/cycle) of continuous therapy with midostaurin or placebo twice daily at 50 mg. Patients who underwent HSCT after achieving CR or CRi with adequate blood count recovery will receive midostaurin or placebo twice daily 50 mg post-transplant therapy, continuously, for up to 12 cycles (28 days/cycle). Post HSCT post-consolidation therapy will begin >30 days but not later than 100 days following HSCT.
 
Follow-up phase:

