Similarly, suppression of the kinase activity in residual leukemic blasts in AML with non-mutated but overexpressed FLT3 during 12 month maintenance treatment with midostaurin may improve the DFS after completion of the induction and consolidation therapy. During the maintenance phase patients will be followed in 3-months intervals for MRD as well as 3 months after completion of the maintenance therapy. Since a strong relationship between the presence of MRD and subsequent relapse was demonstrated in several studies in AML MRD might be a surrogate marker of the likelihood of relapse during and after maintenance and quantitative changes of MRD may indicate effectiveness of maintenance therapy.

It has been demonstrated that allogeneic HSCT does not cure all patients with AML with or without mutated FLT3 as MRD may persist and relapses occur at substantial frequencies ([Christopeit et al 2014](#)). The interim analysis of a single arm study in AML FLT3-mutated demonstrated that midostaurin can be safely administered after allogeneic transplant. Patients received midostaurin during induction, consolidation and after transplant. EFS at 2 years after start of treatment was substantially improved from 25% to 34.6% compared to historical controls. The relative contribution of each phase of treatment (induction, consolidation if applicable, HSCT and post-consolidation) could not be determined (PKC412ADE02T Interim Study Report June 2016, on file). In this study patients can start post-consolidation treatment after allogeneic HSCT and recovery from the procedure. MRD measurements during and after post-consolidation treatment may help to determine whether midostaurin can reduce the residual leukemic disease load in MRD-positive patients after allogeneic transplant and convert the MRD status to negative and/or reduce the rate of molecular and hematologic relapses in MRD-negative transplanted patients. Such findings would support the hypothesis that midostaurin after allogeneic HSCT could ultimately result in a longer DFS after transplant.

The study design will assess the use of midostaurin in combination with standard remission induction chemotherapy, with intermediate dose cytarabine during consolidation, and as a single agent during 12 cycles of post-consolidation therapy. Patients who have AML without a FLT3 mutation (neither ITD nor TKD per clinical cut-off $SR < 0.05$) will be randomly assigned in a 1:1 ratio to midostaurin or placebo arm.

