4.2.2 Consolidation phase

Patients achieving CR or CRi with adequate blood count recovery after induction with one or two cycles of induction therapy will proceed to consolidation therapy with either 3 or 4 cycles of intermediate-dose cytarabine respectively, or to HSCT with or without preceding consolidation cycles. Patients may undergo transplantation at the discretion of the Investigator (refer to 2017 ELN and 2016 National Comprehensive Cancer Network (NCCN) recommendations). In patients who are treated with allogeneic HSCT instead of consolidation therapy or after start of consolidation therapy the conditioning regimen and management after transplantation will be according to local institutional standards. Study treatment will be interrupted at least 48 hours before the initiation of the transplant conditioning regimen. Patients with transplantation and recovery from the procedure will not receive further cycles of consolidation treatment but receive post-consolidation treatment with study drug. They can start the post-consolidation therapy not earlier than 30 days after transplant but not later than 100 days after transplant.

Patients will receive midostaurin (two 25 mg capsules) or placebo (2 capsules) twice daily orally from day 4 until 48 hours prior to the start of the next consolidation cycle.

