- **Study drug (midostaurin** 50 mg [two 25 mg capsules] **or placebo** [2 capsules]) will be administered twice per day by mouth on Days 4 until 48 hrs prior to start of next consolidation cycle (i.e. the morning of Day 27 if hematopoiesis recovers timely (cycle length of 28 days) or later if the cycle needs to be prolonged for blood count recovery). .

Post-consolidation therapy (12 cycles)

Patients who maintain CR or CRi with adequate blood recovery (by bone marrow aspirate/biopsy and peripheral blood evaluation) after completing consolidation therapy will receive 12 cycles (28 days/cycle) of midostaurin/placebo post-consolidation therapy.

Prior to initiation of midostaurin/placebo post-consolidation therapy, all significant acute toxicity from consolidation therapy must have resolved to <grade 2 or be stable except alopecia of any grade. Midostaurin/placebo post-consolidation therapy will begin after partial platelet recovery (platelets \geq 50,000/ μ L) from remission consolidation.

- **Study drug (midostaurin 50 mg [two 25 mg capsules] or placebo [2 capsules])** will be administered twice per day by mouth for 28 consecutive days. Patients should take their doses at approximately the same time each day, and approximately 12 hours should elapse between the morning and evening doses. On days that PK samples are obtained, the patient should take midostaurin/placebo during the clinic visit after the pre-dose PK samples and prior to post-dose PK samples, when instructed by the study staff.

[figure not shown]
Hematopoietic stem cell transplantation

Patients who underwent HSCT after achieving CR or CRi with adequate blood count recovery will receive midostaurin or placebo 50 mg twice daily as post-consolidation therapy, continuously, for up to 12 cycles (28 days/cycle). Post HSCT post-consolidation therapy will begin >30 days following HSCT and adequate blood count recovery but not later than 100 days following HSCT.

Table 6-1 Dose and treatment schedule

Study phase	Study treatments	Pharmaceutical form and route of administration	Dose	Frequency and/or Regimen
Induction 1	Cytarabine	CIVI	200 mg/m ² /day	Day 1-7 (168 hour infusion)
	Daunorubicin	Intravenously by IV push or short (30 minute) infusion	60 mg/m ² /day (irrespective of age)	Day 1-3
	Or Idarubicin	Intravenously by IV push or short (30 minute) infusion	12 mg/m ² /day (irrespective of age)	Day 1-3

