7.1 Study flow and visit schedule

Table 7-1 lists all of the assessments and indicates with an “X”, the visits when they are performed. All data obtained from these assessments must be supported in the patient’s source documentation.

The table indicates which assessments produce data to be entered into the clinical database (D) or remain in source documents only (S) (“Category” column). No CRF will be used as a source document.

Allowed visit windows are specified as follows:

- Screening assessments listed below, must occur within 14 days prior to Day 1 as per Table 7-1.
- During each induction and consolidation cycle, PK and ECG assessments must be performed on the specified day. Local measurements of $QTc \geq 480ms$ will be centrally verified on a copy of a high quality recording that includes time and voltage scales.
- All other assessments should not exceed a 5 day window to take into account scheduling over public holidays if not explicitly specified otherwise.

Every effort should be made to follow the schedule outlined in Table 7-1.

[figure not shown]
[figure not shown]

[figure not shown]
Table 7-1 Visit evaluation schedule

A: Screening until end of consolidation phase

[figure not shown]
	Category	Protocol Section	Screening Phase	Induction Phase Cycle 1-2														End of Induction Phase / EOT	Prior to each cycle of Consolidation phase	Consolidation Phase/HSCT Cycle 1-4														End of Consolidation Phase / EOT
Visit name	D		S C R	INDUCTION C1-C2														IND DISPO SITION		CONSOLIDATION C1- C4														CON DISPO SITION
Day of cycle			-14 to -1	1	2	3	4	5	7	8	11	15	18	21	24	27	28		1	2	3	4	8	11	15	17	21	27	28					
Informed consent																																		
Obtain study Informed Consent	D		x																															
IRI																																		
Registration	D		x																															
Randomization: I1, D8: when FLT3 mutation status is confirmed	D									x I1																								

[figure not shown]
	Category	Protocol Section	Screening Phase	Induction Phase Cycle 1 -2	End of Induction Phase / EOT	Prior to each cycle of Consolidation phase	Consolidation Phase/HSCT Cycle 1-4	End of Consolidation Phase / EOT	
Visit name	D		S C R	INDUCTION C1-C2	IND DISPO SITION		CONSOLIDATION C1- C4	CON DISPO SITION	
Day of cycle			-14 to -1	1 2 3 4 5 7 8 11 15 18 21 24 27 28			1 2 3 4 8 11 15 17 21 27 28		
Prior antineoplastic medications	D		x						

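### Section 7.1.3 moves transplanted patients into post-consolidation within 48 hours of the end of consolidation, while four other places set 30 (or more than 30) to 100 days after HSCT

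*Protocol*

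**What the plan says.** The last bullet under visit frequency in Protocol 7.1.3 covers patients in CR, or in CRi with adequate count recovery. It says they "may proceed to HSCT and will enter the post-consolidation phase within 48 hours after the end of the consolidation phase".

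Four other places state when post-consolidation therapy starts after a transplant:

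- Protocol summary (study design) and 4.2.3, in the same words: "Post HSCT post-consolidation therapy will begin >30 days but not later than 100 days following HSCT".
- 4.2.2: "not earlier than 30 days after transplant but not later than 100 days after transplant".
- 6.1.1.1, in its paragraph on transplantation: therapy "will begin >30 days following HSCT and adequate blood count recovery but not later than 100 days following HSCT".

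These four share only the window. Among them, 4.2.2 alone adds a hold before transplant: "Study treatment will be interrupted at least 48 hours before the initiation of the transplant conditioning regimen". Only 6.1.1.1 ties the restart to blood count recovery.

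Other text points the same way. Section 2.4 has study drug interrupted through the procedure and recovery, and says: "In this study patients can start post-consolidation treatment after allogeneic HSCT and recovery from the procedure". Section 6.3.1 exempts transplant from the 28-day limit on interruptions. The footnote to SAP Figure 2-1 places entry to post-consolidation after recovery from HSCT.

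**The concern.** Section 7.1.3 is where a site looks for phase and visit timing, and this is its only bullet about transplanted patients. Read alone, it gives no transplant-specific restart time. Read plainly, with consolidation over before the transplant, it calls for post-consolidation within two days, when 4.2.2 may already require study drug to be held for conditioning.

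A site following the bullet on that reading would depart from 4.2.2, 4.2.3 and 6.1.1.1. A site following those sections would depart from 7.1.3. Section 12 permits no authorized deviations, so neither route is clean on paper. What is at stake is the timing of study drug around transplant and adherence to the protocol. The efficacy inference is not at stake.

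**Working it through.** The plan gives no figure to reproduce, so the check compares the texts and adds one line of arithmetic.

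| Place | Clock starts at | Start of post-consolidation | Recovery condition |
|---|---|---|---|
| 7.1.3, last visit-frequency bullet | end of consolidation phase | within 48 hours | none stated |
| Summary, study design | HSCT | more than 30, up to 100 days | none in that sentence |
| 4.2.2 | HSCT | 30 to 100 days | recovery from the procedure |
| 4.2.3 | HSCT | more than 30, up to 100 days | none in that sentence |
| 6.1.1.1 | HSCT | more than 30, up to 100 days | adequate blood counts |

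**Reading 1: consolidation ends before HSCT.** Let T be the end of the consolidation phase and let HSCT take place d days later, with d ≥ 0.

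- Deadline in 7.1.3: T + 2 days (48 hours).
- Opening of the window in 4.2.2: T + d + 30 days.
- Gap = (d + 30) − 2 = 28 + d days.

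The gap is smallest at d = 0, where it is 28 days. Under the three statements that say more than 30 days, it is strictly more than 28. No value of d lets both rules be met. No length of conditioning is assumed.

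**Reading 2: the consolidation phase includes HSCT and recovery.** Some text supports this. Section 4.2.2, which deals with the consolidation phase, covers transplant and says: "Patients with transplantation and recovery from the procedure will not receive further cycles of consolidation treatment but receive post-consolidation treatment with study drug". A column of Table 7-1 is headed "Consolidation Phase/HSCT Cycle 1-4". If the phase ended inside the 30-to-100-day window, the gap would be 0.

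The difficulty is that the phase has no stated end for these patients. Section 6.1.5 describes consolidation only as 3 or 4 cytarabine cycles of at most 50 days each, without mention of transplant. The 48 hours therefore have no defined start. If the phase were taken to end at recovery on post-transplant day r, the bullet would require entry by day r + 2. That falls before day 30 whenever r + 2 < 30, that is, whenever r < 28. So even this reading agrees with the window only if the phase ends late enough, and nothing in the protocol requires that. The documents give no recovery time, so r is left open.

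**The preceding bullet of 7.1.3** also uses 48 hours, for patients remaining in remission after consolidation therapy. There the clock starts at the last study-drug dose of the last consolidation cycle, not at the end of the phase, so it does not supply the missing starting point.

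**The case against.** The strongest case on the other side has four parts.

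1. **Location.** The bullet sits under visit frequency in Section 7. The heading of 4.2 sends the reader to Section 6 for dosing, 6.3.1 sends transplant interruptions to 6.1.1, and 6.1.1.1 states the full window. A site that follows the dosing section will not go wrong. This stands as a reason to call the matter minor. It does not make the bullet agree with the other sections.
2. **HSCT belongs to consolidation.** The protocol has only three treatment phases, and the summary lists transplant among the things patients do in the consolidation phase, whether or not any consolidation cycle came first. A patient transplanted straight after induction has no consolidation cycle from which to count on the plain reading. This is a fair argument for Reading 2. It also shows that the bullet lacks a usable starting point, because no section says when the phase ends for that patient.
3. **Entering a phase is not starting therapy.** The bullet speaks of entering the phase, while the window governs therapy. However, 4.2.3, which defines the post-consolidation phase, describes it in terms of giving study drug and applies the window there. The SAP footnote likewise uses entry to mean entry after HSCT recovery.
4. **The plain reading is implausible, so nobody would act on it.** It is clearly not what was intended, and the other sections show the intended rule. That limits the likely harm to a query or a misreading. It is not a reason to leave the sentence in place.

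It is also fair to say that the 28 days measure the distance between two instructions, not a consequence for patients.

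**Conclusion.** The point holds. One bullet in 7.1.3 stands against four statements of the post-transplant window. On the plain reading the two rules are at least 28 days apart and cannot both be met. On the alternative reading the gap can be 0, but the 48-hour clock has no defined start.

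The 28-day figure assumes that HSCT takes place on or after the day consolidation ends. The documents give no transplant rate, so no number of affected patients can be stated. The effect is on treatment timing and protocol adherence around transplant. The correction should be made, but it is a small one: the intended rule is recoverable from 6.1.1.1, and no efficacy endpoint, alpha or power changes. The later stop for futility, recorded in the SAP, does not make the protocol text consistent.

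**What to change.** Replace the last visit-frequency bullet of 7.1.3 with a sentence that repeats the 6.1.1.1 rule, for example: *Patients in CR, or in CRi with adequate blood count recovery, may go on to HSCT. For them, post-consolidation therapy starts once blood counts have adequately recovered, more than 30 days and at most 100 days after HSCT (see 6.1.1.1).* This removes the dependence on an undefined end of the consolidation phase for restarting study drug.

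Optional: change the lower limit in 4.2.2, which allows day 30 itself, to more than 30 days so that all four statements match.

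The replacement text would not state when the consolidation phase ends for a transplanted patient, so the end-of-consolidation disposition visit in Table 7-1 would still lack a stated date for these patients. A short clause could settle that at the same time.

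Cost: one wording edit, with one or two optional ones. Design, sample size and analysis are unchanged.
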